10. ASSESSMENT OF ADVERSE EVENTS

Safety precautions, such as the use of highly experienced investigators, frequent office visits, and close monitoring of clinical and laboratory findings (pregnancy tests) have been implemented in the protocol and are specified in the Schedule of Assessments (see Section 4). All unexpected physical examination findings will be captured as Adverse Events (AEs) when deemed medically significant by the investigator. Potential events that are anticipated post-treatment include erythema and pain. Other, less frequent potential events associated with any dermatological PDT include bleeding, crusting, numbness, itching, blistering and dryness, all of which tend to be transient.

A qualified physician associated with the study will be available to assess clinical signs and symptoms that may be indicative of an AE. Any clinical sign or symptom that was not present at baseline and are not included in the expected side effect profile of PDT will be recorded as an AE. AEs may be reported spontaneously by the patient or elicited

through open (non-leading) questioning during each visit and up until the end of the period of observation (week 36; Visit 6).

10.1 METHODS & TIMING OF SAFETY ASSESSMENTS

Adverse events (AEs) will be assessed at every visit. Subjects who have an AE will be monitored with relevant clinical assessments and laboratory tests, as determined by the investigator. Every attempt will be made to obtain the resolution dates for ongoing AEs.

Physical exams will be performed as per the Schedule of Assessments. Any clinically significant physical exam abnormalities will be documented as an AE. Pregnancy testing for females of child bearing potential (FCBP) will be done at screening, baseline, and at week 36. The FCBP will consist of a urine pregnancy test for β -hCG with a sensitivity of at least 50 mIU/ml.

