4.0 SCHEDULE OF ASSESSMENTS

	Treatment Phase		Observational Follow-up Phase			
Visit Number	1 Screening	2 Baseline	3	4	5	6 End of Study/ Early Termination Visit
Week(s)	-2-0 weeks	day 0	6 weeks	12 weeks	24 weeks	36 weeks
Informed Consent	Х					
Medical History	Х					
Demographics	Х					
Inclusion/ Exclusion Criteria	х	х				
Concomitant Medications	Х	Х	х	х	Х	х
Physical Exam	Х	х				х
Treatments		х	Х	Х		
Physician Efficacy Assessments						
Comparison of photographs		х	х	х	х	х
Investigator Global Assessment		Х	х	х	Х	х
Subject Efficacy Assessments						
Subject Global Assessment of Improvement		х	х	х	х	х
DLQI		х	х	х	х	х
Physician Safety Assessments						

Page 11 of 32

		Treatment Phase				Observational Follow-up Phase	
Visit Number	1 Screening	2 Baseline	3	4	5	6 End of Study/ Early Termination Visit	
Week(s)	-2-0 weeks	day 0	6 weeks	12 weeks	24 weeks	36 weeks	
Swelling, Vesiculation, Erosion, Erythema, Flaking, Crusting		х	х	х	х	х	
Hyperpigmentatio n		х	х	х	х	х	
Adverse Events		х	х	х	х	х	
Pregnancy Testing ^d	х	х				х	
Subject Safety Assessments							
Redness, swelling, and dryness		х	х	х	х	Х	
Pain (VAS Scale)		х	х	х	х	Х	
Photographs		Х	х	Х	Х	Х	

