7.2.2 EXCLUSION CRITERIA

- Inability to provide voluntarily consent or mentally incompetent
- No active herpes labialis lesions
- Subjects with any condition which places the subject at unacceptable risk if he/she were to participate in the study, or confounds the ability to interpret data from the study
- Subjects with any other skin condition that might affect the evaluation of the study disease
- Pregnant or breastfeeding female subjects

- Subjects who have used any investigational medication within one month prior to study entry
- Subjects who have been previously exposed to PDT and/or topical Levulan® therapy
- Subjects who have used local therapy (e.g. cryotherapy) or topical treatment (e.g.
 5% fluorouracil) within three months of study entry
- Subjects who have used an oral photosensitizing drug (e.g. Declomycin®) within six months of study entry
- Subjects who are currently using photosensitizing agents (e.g. thiazides, tetracyclines, fluoroquinolones, phenothiazines, and sulfonamides) because of the risk of augmented photosensitivity
- Subjects who are frequently exposed to ultraviolet radiation (e.g. lifeguards, construction workers, frequent sunbed users, etc.)
- Subjects with a history of cutaneous photosensitization, porphyria, hypersensitivity to porphyrins, or photodermatosis
- Subjects with a known hypersensitivity to δ -aminolevulinic acid
- Subjects who are immunocompromised

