7.3 VISIT SCHEDULE & ASSESSMENTS

The study will consist of a screening visit, up to three scheduled treatments, and two scheduled office visits. There can be a three-day window period for each scheduled visit in order to accommodate the subject's schedule and unforeseen scheduling conflicts.

- Visit 1 (Screening): Subjects can be screened for the study up to two weeks before Visit 2 (Baseline). During screening, the study will be reviewed, written informed consent obtained, and eligibility confirmed. If applicable, the washout from prohibited medications or treatments will be determined at this visit.
- 2. Visit 2 (Baseline): Following signed, written informed consent and confirmation of eligibility, all subjects will have their lips photographed. Medical history, dermatologic exam, urine pregnancy test (if applicable), review of concomitant medications, clinical evaluations, and tolerability assessments will be performed at this visit. Study medication application to clean skin will be followed by a ninety minute incubation period under occlusion. Subsequently, patients will be exposed to blue light therapy for 16 minutes and 40 seconds. Post-therapy

- assessments will be performed afterwards, as well as education on appropriate sun protection methods.
- 3. Visits 3-4: Subjects will return every six weeks for up to two additional treatments. Treatment will be discontinued once the patient has achieved clinical clearance. Tolerability assessments, study medication application, blue light therapy, post-therapy assessments, and photographs will be performed.
- 4. Visit 5-6 (End of Study): Subjects will return 12 and 24 weeks after the last treatment for clinical evaluations, tolerability assessments, and photographs.

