10.2.6 PREGNANCIES

Pregnancies and suspected pregnancies (including a positive pregnancy test regardless of age) of a female subject or the female partner of a male subject occurring while the

subject is in the study are considered immediately reportable events. Study treatments will be stopped immediately if this occurs.

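### No pregnancy test is scheduled before the second and third treatments, so re-treatment rests on a baseline test about 6 or 12 weeks old

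*Combined protocol and SAP*

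**What the plan says.** Section 7.2.2 lists among the exclusions "Pregnant or breastfeeding female subjects". Section 10.2.6 makes known and suspected pregnancies, including any positive test, immediately reportable and adds: "Study treatments will be stopped immediately if this occurs".

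Section 10.1 gives the timing of the tests: "Pregnancy testing for females of child bearing potential (FCBP) will be done at screening, baseline, and at week 36". The test is a urine hCG assay. In the Section 4 schedule, the row "Pregnancy Testing" is marked at Visits 1, 2 and 6 (Visit 6 doubles as the early-termination visit), while the treatment row is marked at Visits 2, 3 and 4.

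Section 7.3 names a urine pregnancy test among the Visit 2 procedures. For Visits 3 and 4 it says: "Tolerability assessments, study medication application, blue light therapy, post-therapy assessments, and photographs will be performed". No pregnancy test appears there. The same section allows some slack in dates: "There can be a three-day window period for each scheduled visit".

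Outside the scheduled tests, Section 10 relies on "open (non-leading) questioning during each visit", and Section 9.3.4 adds a telephone call two days after each treatment. Section 10.1 lets the investigator order laboratory tests for a subject who has an adverse event.

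**The concern.** The protocol intends that pregnant women are not treated, at entry or later. At entry the intention is backed by two tests. For the later exposures it is backed by none, although drug, light dose and procedure are the same. Followed to the letter, the plan re-treats a woman of child-bearing potential on a result from day 0.

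The protocol's own conduct at entry is stricter. Screening falls at most two weeks before baseline, yet the test is repeated at baseline. A result up to 14 days old is thus not relied on alone for the first treatment, while one of 42 or 84 days is accepted for the second or third. No reason is given for the difference.

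At stake is exposure of a woman with an early pregnancy that she has not recognised. The eligibility lists in Sections 7.2.1 and 7.2.2 set no contraception requirement that would make this less likely.

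**Working it through.** **Inputs**

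- Treatments: up to three, six weeks apart (Sections 7.3 and 7.4), so days 0, 42 and 84.
- Scheduled tests: screening, day 0 and Visit 6 (Sections 4 and 10.1).
- Visit window: three days (Section 7.3), taken here as plus or minus 3 days. The protocol does not give the direction, so this is an assumption.
- Sample size: 20 (Section 7.2). The number of women of child-bearing potential is not stated.

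The plan gives no figure of its own on this point to reproduce.

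**Age of the last scheduled test at re-treatment** = treatment day − day of last test

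| Treatment | Nominal | Window around the nominal date | Window run from the previous visit |
|---|---|---|---|
| Second (Visit 3) | 42 − 0 = 42 days | 42 ± 3 = 39 to 45 | 39 to 45 |
| Third (Visit 4) | 84 − 0 = 84 days | 84 ± 3 = 81 to 87 | 84 ± 6 = 78 to 90 |

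The number of scheduled tests after day 0 and up to the last treatment is 0.

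**When the next scheduled test falls.** Without early termination it is at Visit 6.

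- By Section 7.3, Visit 6 is 24 weeks after the last treatment, however many were given.
- If week 36 in Section 10.1 is read as a fixed date, the gap after the last treatment is 36 − 12 = 24 weeks (three treatments), 36 − 6 = 30 weeks (two) or 36 − 0 = 36 weeks (one).

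On either reading the test comes after all treatment, so its result cannot stop an exposure.

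**What else could trigger the stop rule**

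- Open questioning finds what the woman already knows or suspects.
- The telephone call comes 42 − 2 = 40 days before the next treatment. It asks about redness, swelling, dryness and any problems since the visit.
- Discretionary laboratory tests are described for subjects who have an adverse event.

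None of these would be expected to find an unrecognised pregnancy without symptoms.

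**Number of exposures affected.** For each woman of child-bearing potential, the re-treatments without a same-visit test are 0, 1 or 2 for one, two or three treatments. Over the trial the bounds are 0 and 2 × 20 = 40. The upper bound requires all 20 subjects to be in this group and all to receive three treatments.

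**The case against.** The strongest reply is that the timing is a consistent design choice rather than a contradiction. Sections 4 and 10.1 match. The stop rule does not need a positive test, because suspicion is enough, and subjects are questioned at every visit. Exposure is topical, confined to the lips, given in the clinic and limited to three occasions. The protocol describes no embryo-fetal risk and does not say that a test is needed before each dose; its introduction says that the therapy appears to have no systemic side effects. The group concerned may be very small: both sexes are eligible, there is no upper age limit, and a subject cleared after one treatment is not re-treated. The 0 to 40 range is only a logical bound.

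Two points of evidence also need care. The Visit 3-4 list in Section 7.3 is not exhaustive, since it omits other assessments that Section 4 schedules at those visits; its silence on pregnancy testing adds little. The pregnancy row in Section 4 carries a footnote marker whose text was not in the copy reviewed, and the consent pages, which might mention contraception, were not available either.

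Most of this stands as a limit on size. None of it supplies a test before re-treatment. Section 10.1 states the timing in full, so the missing footnote is unlikely to change the reading. A contraception statement in the consent form would lower the risk but would not replace a test. The point does not depend on proven fetal harm: the protocol itself chose to exclude pregnancy and to stop for it, and Section 10 counts pregnancy tests among its safety precautions.

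**Conclusion.** The concern holds. By the scheduled visits, a woman of child-bearing potential receives her second treatment on a test 42 days old (39 to 45 with the window) and her third on one 84 days old (81 to 87, or 78 to 90 if the windows accumulate). No scheduled result can activate the stop rule before a later exposure. The gap is confined to unrecognised pregnancy, begun after the baseline test, in women who are re-treated. How many such women there will be cannot be derived from the protocol and could be none.

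The day counts assume treatment at the nominal six-week interval and a symmetric three-day window. The point concerns participant safety only; the clearance endpoint, the sample size and the analysis are unaffected. It should be fixed because the protocol's own rule calls for it and the cost is slight.

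**What to change.** At Visits 3 and 4, whenever treatment is to be given, perform the urine hCG test already specified in Section 10.1 in females of child-bearing potential, and read the result before study drug is applied. Amend four places to match: the pregnancy-testing row in Section 4, the Visit 3-4 procedures in Section 7.3, the same list in the synopsis, and the timing sentence in Section 10.1. The last test would then be 0 days old at every treatment.

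The cost is at most two extra urine tests per woman of child-bearing potential, and at most 2 × 20 = 40 in the trial even if every subject were in that group. No new visit or type of procedure is needed. The only other consequence is an occasional deferred or stopped treatment.

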10.2 RECORDING & REPORTING OF ADVERSE EVENTS 10.2.1 ADVERSE EVENTS

An AE is any noxious, unintended, or untoward medical occurrence that may appear or worsen in a subject during the course of a study. An AE may be a new concurrent illness, a worsening concomitant illness, an injury, or any concomitant impairment of the subject's health, including laboratory test values (as specified by the criteria below), regardless of etiology. Any medical condition that was present prior to study treatment and remains unchanged or improved should not be recorded as an AE. If there is a worsening of an established medical condition (aside from the expected treatment side effects), this should be considered an AE. Individual signs and symptoms of an AE should be recorded on the AE page of the subject's source documents. All AEs will be recorded by the investigator(s) from the time the informed consent form is signed through the end of the designated follow-up period (week 36; Visit 6).

10.2.2 SERIOUS ADVERSE EVENTS

A serious adverse event (SAE) is any AE which:

- Results in death
- Is life-threatening (i.e. in the opinion of the investigator, the subject is at immediate risk of death from the AE)

- Requires inpatient hospitalization or prolongation of an existing hospitalization
- Results in persistent or significant disability/incapacity (a substantial disruption of the subject's ability to conduct normal life functions)
- Results in a congenital anomaly/birth defect
- Constitutes an important medical event

Important medical events are defined as those occurrences that may not be immediately life threatening or result in death, hospitalization, or disability, but may jeopardize the subject's health or require medical or surgical intervention to prevent one of the other outcomes listed previously. Medical and scientific judgment should be exercised in deciding whether such an AE should be considered serious.

Events not considered to be an SAE are hospitalizations occurring under the following circumstances:

- Hospitalizations planned before entry into the clinical study
- Hospitalizations for elective treatment of a condition unrelated to the studied indication or its treatment
- Hospitalizations that occur on an emergency, outpatient basis and do not result in admission (unless fulfilling the criteria under serious adverse event)
- Hospitalizations that are part of the normal treatment or monitoring of the studied indication and not associated with any deterioration in the condition

If an AE is considered serious, both the AE pages of the CRF and the SAE Report Form must be completed. For each SAE, the investigator will provide information on severity, start and stop dates, relationship to study drug, action taken regarding study treatment, and outcome.

10.2.3 CLASSIFICATION OF SEVERITY

The intensity of all AEs will be graded as *mild, moderate*, or *severe* using the following definitions:

Mild	The adverse event is transient and easily tolerated.
Moderate	The adverse event causes the patient discomfort and interrupts the patient's
	usual activities.
Severe	The adverse event causes considerable interference with the patient's usual
	activities and may be incapacitating or life-threatening.

10.2.4 CLASSIFICATION OF RELATIONSHIP/CAUSALITY OF AE/SAE TO STUDY DRUG

The investigator must determine the relationship between the administration of study drug and the occurrence of an AE/SAE as *not suspected* or *suspected* as defined below:

Not suspected:	The temporal relationship of the adverse event to study drug administration makes a causal relationship unlikely or remote, or other medications, therapeutic interventions or underlying conditions provide a sufficient explanation for the observed event.
Suspected:	The temporal relationship of the adverse event to study drug administration makes a causal relationship possible , and other medications, therapeutic interventions or underlying conditions do not provide a sufficient explanation for the observed event.

10.2.5 REPORT OF ADVERSE EVENTS TO THE INSTITUTIONAL REVIEW BOARD

The Principle Investigator is required to notify the Institutional Review Board (IRB) of a serious adverse events according to institutional policy.

10.2.6 PREGNANCIES

Pregnancies and suspected pregnancies (including a positive pregnancy test regardless of age) of a female subject or the female partner of a male subject occurring while the

subject is in the study are considered immediately reportable events. Study treatments will be stopped immediately if this occurs.

11. PROTOCOL AMENDMENTS/DEVIATIONS

11.1 PROTOCOL AMENDMENTS

Any amendment to this protocol must be agreed to by the Principle Investigator and reviewed by DUSA Pharmaceuticals, Inc. Written verification of Institutional Review Board/Independent Ethics Committee (IRB/IEC) approval will be obtained before any amendment is implemented. Written signed approval from the IRB/IEC should refer specifically to the investigator, protocol number and title, and mention any applicable amendment numbers. Amendments that are administrative in nature do not require IRB/IEC approval, but will be submitted to the IRB/IEC for information purposes.

11.2 PROTOCOL DEVIATIONS

When an emergency occurs that requires a deviation from the protocol for a subject, a deviation will be made only for that subject. A decision will be made as soon as possible to determine whether or not the aforementioned subject is to continue in the study. The subject's medical records will completely describe and explain the protocol deviation. In addition, the Principle Investigator will notify the IRB/IEC in writing of a protocol deviation. Non-emergency, minor deviations from the protocol will be permitted with approval of the Principal Investigator.

12. QUALITY CONTROL & QUALITY ASSURANCE

12.1 ANALYSES & REPORTING

After all 20 patients have completed the 36-week clinical trial, the Section of Biostatistics and Epidemiology at Dartmouth Medical School will help facilitate data analysis, interpretation, and presentation for future publication.

12.2 INVESTIGATOR RESPONSIBILITIES

The investigator(s) will follow the principles of good clinical practice (GCP) and conduct the study in accordance with the principles of the Declaration of Helsinki.

12.3 AUDITS & INSPECTIONS

The Principle Investigator is required to permit direct access to the facilities where the study took place, source documents, CRFs and applicable supporting records of subject participation for audits and inspections by the IRBs/IECs and regulatory authorities (i.e. FDA). The investigator will make every effort to be available for audits and/or inspections.

13. REGULATORY CONSIDERATIONS

13.1 INFORMED CONSENT

Documentation that informed consent occurred prior to a subject's entry into the study and of the informed consent process should be recorded in the subject's source documents. The original consent form signed and dated by the subject and the person consenting the subject must be maintained in the Principle Investigator's study files. A copy of the informed consent form will be given to the subject.

13.2 STUDY RECORDS REQUIREMENTS

The Principle Investigator must ensure that the records and documents pertaining to the conduct of the study and the distribution of the study drug be retained by the investigator for as long as needed to comply with national regulations (generally two-three years after discontinuing clinical development). The Principle Investigator agrees to adhere to the document/records retention procedures by signing the protocol. The following are examples of pertinent records and documents:

- Copies of CRFs and source documents
- Hospital records
- Clinical and office charts
- Laboratory notes
- Memoranda
- Subject's evaluation checklists
- Pharmacy dispensing records
- Recorded data from automated instruments
- Copies or transcriptions certified after verification as being accurate copies
- Microfiches
- Photographic negatives, microfilm, or magnetic media
- Subject files

- Records kept at the pharmacy, laboratory, and medico-technical departments involved in the clinical study
- Documents regarding subject treatment and study drug accountability
- Original signed informed consent forms

15. ABBREVIATIONS

AE: Adverse Events

ALA: Aminolevulinic Acid

CRF: Case Report Form

DLQI: Dermatological Life Quality Index

FCBP: Females of Child Bearing Potential

GCP: Good Clinical Practice

IEC: Independent Ethics Committee

IRB: Institutional Review Board

PDT: Photodynamic Therapy

SAE: Severe Adverse Events

SPF: Sun Protection Factor

VAS: Visual Analogue Scale
